11.3.1.2 Laboratory Data

Laboratory data will be listed by patient. Values above and below normal ranges will be indicated, and whether clinically significant. All laboratory values will be graded according to the NCI-CTCAE version 4.03 criteria. Laboratory data will be summarized by actual value and change from baseline using number of non-missing observations (n), mean, standard deviation, median, minimum and maximum. In addition, shift tables and the incidence of Grade 3 or 4 laboratory values will be presented.

11.3.1.3 Vital Signs

Vital signs will be listed by patient. Values above and below normal ranges will be indicated as will clinical significance. Vital sign data will be summarized by actual value and change from baseline using number of non-missing observations (n), mean, standard deviation, median, minimum and maximum.

11.3.1.4 Other Safety Data

Data collected for physical examinations, ECGs and related measures will be listed.

11.3.2 Efficacy Analyses

11.3.2.1 Primary Efficacy Endpoint

The primary efficacy endpoint is the proportion of patients in each disease cohort (cholangiocarcinoma, gallbladder carcinoma, urothelial carcinoma, or other solid tumor) with objective response (OR) within 4 cycles of study drug. Thus, this is the proportion of patients in Cohorts 1-12 with an OR within 16 weeks of their first dose of study drug and the proportion of patients in Cohort 13 with an OR within 12 weeks of their first dose of study drug. The OR rate is defined as the proportion of patients in the FAS with a confirmed complete or partial response. Ninety percent confidence intervals for the OR rate will be estimated.

11.3.2.2 Secondary Efficacy Endpoints

Duration of response, duration of SD, PFS and OS curves will be estimated by disease cohort using Kaplan-Meier product limit estimates. Median and 90% confidence interval of time-to-event will be estimated. Progression-free survival will be calculated from the date of first dose of study drug to the date of first documented evidence of disease progression or death, whichever is earlier. Overall survival will be calculated from the date of first dose of study drug to the date of death due to any cause. Patients who did not experience progression or death will be censored at the time of last contact.

11.3.3 Pharmacokinetic Endpoint Analysis

Mean plasma concentrations of FF-10502 will be determined at each time point by dose cohort for evaluation of dose-linearity. Because a limited number of plasma concentrations will be determined, full determination of routine PK parameters may not be possible. In addition to mean plasma concentrations, as the data allow, additional PK analyses will be provided (trough levels, $t_{1/2}$, T_{max} , C_{max} , AUC, etc). Population PK methods will be utilized to characterize the PK profile of FF-10502.

11.3.4 Pharmacodynamic Endpoint Analysis

Pyrimidine nucleoside anti-metabolites exert their activity via cell-cycle specific cell killing, through incorporation into cellular DNA of the target cancer cell. Thus, cells undergoing DNA synthesis (S-phase) are killed, and the progression of cells through the G1/S-phase boundary is blocked. Accordingly, FF-10502 incorporation into the cellular DNA of whole blood will be

determined as a pharmacodynamic endpoint in this study. Change from baseline in FF-10502 cellular DNA incorporation levels will be measured in whole blood collected from each patient during the study. pharmacodynamic parameters from the PD population will be summarized using descriptive statistics including the number of patients, mean, standard deviation, minimum, median, maximum, range, and coefficient of variation. Changes from baseline will be correlated with drug exposure and clinical outcome.

11.3.5 Other Summaries

Demographics will be summarized using descriptive statistics. Medical history findings, concomitant medications, and protocol deviations will be listed but not summarized.

12 STUDY MANAGEMENT

12.1 Data Management

The investigator is responsible for completing and maintaining adequate and accurate source documentation. Source documentation constitutes original records, which may include: progress notes, medication administration records, laboratory reports, ECG tracings, discharge summaries, CRF worksheets, etc. Data for this study will be submitted electronically. Access to the database will be provided following a brief on-line training session. Each user will receive a unique username and password, which should not be shared. The investigator must sign the investigator's statement for each patient indicating that the data reported are accurate. See APPENDIX H for Ethical Standards to be followed during the study.

12.2 Monitoring

The sponsor and Westat are responsible for ensuring the proper conduct of the study with regard to ethics, protocol adherence, site procedures, integrity of the data, and applicable laws and/or regulations. At regular intervals during the study and following completion of the study, the sponsor's study monitors will contact the study site via visits to the site, telephone calls, and letters in order to review study progress, CRF completion, and address any concerns or questions regarding the study conduct. During monitoring visits, the following aspects of study conduct will be carefully reviewed: informed consent of patients, patient recruitment, patient compliance with the study procedures, source data verification, drug accountability, use of concomitant therapy by patients, AE and SAE documentation and reporting, and quality of data. Records pertaining to these aspects are expected to be kept current.

12.3 Audits and Inspections

The sponsor, Westat, a regulatory authority, or an IRB may visit the study site at any time during the study or after completion of the study to perform audits or inspections. The purpose of a sponsor audit or regulatory inspection is to systematically and independently examine all study-related activities and documents to determine whether these activities were conducted according to the protocol, GCP, ICH guidelines, and any other applicable regulatory requirements. Investigators should contact FPHU/Westat immediately if contacted by a regulatory agency about an inspection at their site.

12.4 Amendments

Any amendments to the protocol will be written and approved by the sponsor. All amendments must be submitted to the IRB for approval prior to implementing the changes. In some instances, an amendment requires changes to the informed consent form, which also must be submitted for IRB approval prior to administration to patients. If any changes to the CRF are required, Westat will issue supplemental or revised CRF pages on behalf of the sponsor.

12.5 Record Keeping

12.5.1 Health Insurance Portability Accountability Act of 1996

The investigator agrees to comply with all applicable federal, state, and local laws and regulations relating to the privacy of patient health information, including, but not limited to, the Standards for Individually Identifiable Health Information, 45 CFR. Parts 160 and 164 (the Health Insurance Portability Accountability Act of 1996 [HIPAA] Privacy Regulation). The investigator shall ensure that study patients authorize the use and disclosure of protected health

information in accordance with HIPAA Privacy Regulation and in a form satisfactory to the sponsor. See APPENDIX I for Investigator Obligations.

12.5.2 Financial Disclosure

The investigator shall provide to the sponsor sufficient accurate financial information to allow the sponsor and Westat to submit complete and accurate financial certification or disclosure statements to the FDA. The investigator shall promptly update this information if any relevant changes occur in the course of the study or for one year following completion of the study.

12.5.3 Access to Original Records

It is an expectation of regulatory authorities that monitors, auditors, and representatives of national and international government regulatory agency bodies have access to original source documentation to ensure data integrity. "Original" in this context is defined as the first documentation of an observation and does not differentiate between hard copy and electronic records.

12.5.4 Retention of Study Documents

Study-related records must be retained for at least 2 years after the last approval of a marketing application in an ICH region and until there are no pending or contemplated marketing applications in an ICH region, or at least 2 years have elapsed since the formal discontinuation of clinical development of the investigational product. These documents should be retained for a longer period, however, if required by applicable regulatory requirements or by an agreement with the sponsor.

The investigator must not destroy any study-related records without receiving approval from the sponsor. The investigator must notify the sponsor in the event of accidental loss or destruction of any study records. If the investigator leaves the institution where the study was conducted, the sponsor must be contacted to arrange alternative record storage options.

13 ADMINISTRATIVE STRUCTURE OF THE STUDY

Westat will be responsible for data management, statistical analyses, and clinical study report writing. Clinical monitors under the direction of Westat will be used to monitor the study. Clinical laboratory parameters will be assessed by local laboratories and results recorded in the CRF module.

15 APPENDICES

APPENDIX A. Eastern Cooperative Group (ECOG) Performance Status Scale

ECOG PERFORMANCE STATUS*	
Grade	ECOG
0	Fully active, able to carry on all pre-disease performance without restriction
1	Restricted in physically strenuous activity but ambulatory and able to carry out work of a light or sedentary nature, e.g., light house work, office work
2	Ambulatory and capable of all selfcare but unable to carry out any work activities. Up and about more than 50% of waking hours
3	Capable of only limited selfcare, confined to bed or chair more than 50% of waking hours
4	Completely disabled. Cannot carry on any selfcare. Totally confined to bed or chair
5	Dead

* From ECOG, [name], Group Chair

APPENDIX B. New York Heart Association (NYCA) Classification for Heart Failure**NYHA Classification - The Stages of Heart Failure**

Class	Patient Symptoms
Class I (Mild)	No limitation of physical activity. Ordinary physical activity does not cause undue fatigue, palpitation, or dyspnea (shortness of breath).
Class II (Mild)	Slight limitation of physical activity. Comfortable at rest, but ordinary physical activity results in fatigue, palpitation, or dyspnea.
Class III (Moderate)	Marked limitation of physical activity. Comfortable at rest, but less than ordinary activity causes fatigue, palpitation, or dyspnea.
Class IV (Severe)	Unable to carry out any physical activity without discomfort. Symptoms of cardiac insufficiency at rest. If any physical activity is undertaken, discomfort is increased.

APPENDIX C. FF-10502-01 Dosing Delays and Dose Modifications

Treatment may be delayed up to 14 days. If the patient has completed two cycles and, in the investigator's opinion, is receiving benefit, treatment may be delayed for longer than 14 days and then resumed following a discussion with the Medical Monitor. Patients who require the next treatment cycle to be held for more than 14 days due to ongoing toxicity from the prior cycle should have the dose reduced by 25%.

Patients who experience a toxicity requiring reduction in dose level may continue treatment at the lower dose level until disease progression or unacceptable toxicity. The dose level may be reduced twice in 25% decrements. For example, if the starting dose was 90 mg/m², then first dose reduction is 67.5 mg/m², and the 2nd dose reduction is 50 mg/m². Patients who continue to require dose modifications beyond this should be discontinued from the trial. Once the dose has been reduced it may not be escalated.

If a patient experiences myelosuppression, FF-10502-01 should be held and restarted according to Table 1.

Table 1. Dose Modification for Myelosuppression

Absolute Granulocyte Count (x 10⁶/L)		Platelet Count (x 10⁶/L)	Action
≤ 1000 (Grade 3 or 4)	Or	≤ 50,000 (Grade 3 or 4)	Dose is held until recovery to Grade 2 or better
Upon recovery to			
→1000 (Grade 2, 1 or normal)	And	>50,000 (Grade 2, 1 or normal)	Dose may be 75% or 100% of recommended dose at investigator discretion

Table 2. Dose Modifications for Non-Hematologic Toxicity

Non-Hematologic Toxicity	Modification
Grade ≥ 3 lasting ≤ 7 days	Withhold dose until ≤ Grade 1, resume next dose at 100%
Grade ≥ 3 lasting > 7 days	Withhold dose until ≤ Grade 1, resume next dose with a 25% reduction

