8.4.2 Instructions Regarding Dose Delays and Dose Modifications

Adverse events considered for treatment interruption and dose reduction will exclude the events assessed by the investigator as exclusively related to underlying disease or medical condition/concomitant treatment. If treatment must be delayed for reasons other than toxicity, contact the Medical Monitor to discuss the reasons for delay and plans for resuming study therapy.

- Treatment may be delayed up to 14 days. If the patient has completed two cycles and, in the investigator's opinion, is receiving benefit, treatment may be delayed for longer than 14 days and then resumed following a discussion with the Medical Monitor. Patients who require the next treatment cycle to be held for more than 14 days due to ongoing toxicity from the prior cycle should have the dose reduced by 25%.

- Patients who experience a toxicity requiring reduction in dose level may continue treatment at the lower dose level until disease progression or unacceptable toxicity. The dose level may be reduced twice. Patients who continue to require dose modifications beyond this should be discontinued from the trial. Once the dose has been reduced it may not be escalated.
- See [APPENDIX C](#) for FF-10502-01 dose modification requirements.

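### Appendix C Table 1 permits a full-dose restart after a long myelosuppression hold where the text calls for a 25% reduction, and no precedence is stated

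*Protocol*

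**What the plan says.** Two sets of restart instructions apply to the same patient.

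**The text.** Protocol Section 8.4.2 covers a patient whose next cycle is "held for more than 14 days due to ongoing toxicity from the prior cycle should have the dose reduced by 25" percent. The opening paragraph of Appendix C repeats the rule. Neither place exempts hematologic toxicity. Delays are otherwise limited to 14 days, with an exception: "If the patient has completed two cycles and, in the investigator's opinion, is receiving benefit, treatment may be delayed for longer than 14 days", and resumption then follows a discussion with the Medical Monitor. Appendix C allows two reductions and illustrates them: "For example, if the starting dose was 90 mg/m², then first dose reduction is 67.5 mg/m², and the 2nd dose reduction is 50 mg/m²". It adds that "Patients who continue to require dose modifications beyond this should be discontinued from the trial", and that a reduced dose may not be raised again.

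**The table.** Appendix C then states: "If a patient experiences myelosuppression, FF-10502-01 should be held and restarted according to Table 1". Table 1 holds the drug while granulocytes or platelets are at Grade 3 or 4. Once both have recovered to Grade 2 or better, "Dose may be 75% or 100% of recommended dose at investigator discretion". It does not mention how long the hold lasted.

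No sentence in Section 8.4.2 or Appendix C ranks the text above the table or the table above the text.

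**The concern.** Myelosuppression that holds the next cycle for more than 14 days falls under both rules. The text points to one restart dose, a 25% cut. Table 1 points to two, and one of them is the full dose. An investigator who restarts from Table 1 can cite the appendix for 100%, and one who restarts from the paragraph above it can cite the same page for 75%.

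What is at stake is consistent dosing and the safety of a small group whose counts recover slowly. These are the patients for whom the text asks for caution.

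A secondary wording problem adds to this. Table 1 takes its percentages from a *recommended dose*, a term used nowhere else on its own and not defined in the text reviewed. The nearest defined term is the recommended Phase 2 dose, which Section 8.5 gives as 90 mg/m².

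**Working it through.** **Inputs**
- Phase 2a dose: 90 mg/m², on Days 1, 8 and 15 of 28 in Cohorts 10 to 12 and on Days 1 and 8 of 21 in Cohort 13 (Protocol Section 8.2).
- Reduction step: 25%, at most twice (Section 8.4.2, Appendix C).
- Table 1 restart: 75% or 100%.

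**Step 1. Reproduce the protocol's own example.**
- First reduction: 90 × 0.75 = 67.5 mg/m², as stated.
- Second reduction: 67.5 × 0.75 = 50.6 mg/m², stated as 50 after rounding.
- The steps therefore compound. Two cuts of 25% of the starting dose would give 90 × 0.50 = 45, which does not match.

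**Step 2. Compare the two rules for a patient at 90 mg/m² whose next cycle is held more than 14 days for low counts.**

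| Rule | Restart dose (mg/m²) |
|---|---|
| Section 8.4.2 and Appendix C text | 67.5 |
| Appendix C Table 1 | 67.5 or 90 |

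Ratio of the highest permitted restart to the text dose: 90 / 67.5 = 1.33.

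**Step 3. Express this as dose per week.**
- Cohorts 10 to 12: 3 × 90 / 4 = 67.5 against 3 × 67.5 / 4 = 50.6 mg/m² per week.
- Cohort 13: 2 × 90 / 3 = 60 against 2 × 67.5 / 3 = 45 mg/m² per week.

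**Step 4. How slow must recovery be?** Assume the last scheduled dose of the cycle was given on its nominal day.
- Cohorts 10 to 12: the next cycle is due on Day 29, a 14-day hold ends on Day 43, and the last dose was on Day 15, so 43 − 15 = 28 days.
- Cohort 13: the next cycle is due on Day 22, a 14-day hold ends on Day 36, and the last dose was on Day 8, so 36 − 8 = 28 days.

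In either schedule, a hold driven by Table 1 counts must still be at Grade 3 or 4 more than 28 days after the last dose. Section 8.5 allows granulocyte growth factors after Cycle 1, which makes this less likely for neutrophils. The documents give no frequency.

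**Step 5. Which reference dose can Table 1 mean?**
- *RP2D (90 mg/m²).* A patient already reduced to 67.5 would be offered 100% of 90, an increase that the no-escalation rule forbids.
- *Current dose.* The same patient would be offered 67.5 or about 50, and neither is an increase.
- For a Phase 2a patient not yet reduced, both readings give 90.

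Only the current-dose reading is consistent with the rest of the appendix. It leaves the conflict in Step 2 in place.

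**The case against.** The best defence is that Table 1 only permits, while the long-hold sentence restricts. Read together, the table offers 75% or 100% in general, and the text removes 100% in one sub-case. Choosing 75% satisfies both, at least until two reductions have been used. The route to a long hold is also guarded by the conditions of two completed cycles, perceived benefit and a Medical Monitor discussion. Anyone restarting from Table 1 alone has passed over the paragraph that allows the restart at all.

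Much of this stands, and it is why the point is minor. It does not remove the gap:
- Appendix C directs the restart after myelosuppression to Table 1.
- Preferring the more specific rule does not decide the matter: the text is specific on length of hold, the table on type of toxicity.
- Table 2, for non-hematologic toxicity, does separate short from long events. A reader could therefore take the lack of a time limit in Table 1 as deliberate.
- The Medical Monitor is not told which rule prevails or whether the 25% cut may be waived.

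A reader might infer more than the documents support:
- *That Table 2 has the same conflict in its full-dose row.* This holds only if the seven-day limit counts time at Grade 3 or above and later recovery to Grade 1 takes the hold past 14 days. If it counts the whole episode, there is no conflict.
- *That Table 1 authorises a return to 90 mg/m² after a reduction, or a third cut (50 × 0.75 = 37.5 mg/m²).* The text bars both, through the no-escalation rule and the limit of two reductions.
- *That patients at other Phase 1 dose levels are at risk now.* Section 6.3 describes Phase 1 accrual in the past tense, and Phase 2a is fixed at 90 mg/m².

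**Conclusion.** The inconsistency is real and minor. For next-cycle holds of more than 14 days caused by myelosuppression, Table 1 permits 90 mg/m² where the text calls for 67.5, a ratio of 1.33, and the documents do not say which governs.

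It would go too far to say that the two rules cannot both be followed: before the second reduction, a 75% restart complies with each. Nor is there a statistical consequence to claim. No sample size, power, MTD or RP2D figure depends on it. SAP Section 3.4.1 computes dose intensity from the volume administered, so the exposure summaries will show what patients received.

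The conclusion on the 14-day rule rests only on the wording of Section 8.4.2 and Appendix C. The point about *recommended dose* is less certain: the Dose Rationale (Section 4.5) was not in the text available for review, so a definition there cannot be ruled out.

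**What to change.** Make two edits to Appendix C in the next amendment:

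1. In Table 1, replace *recommended dose* with *the patient's current dose*.
2. Add a note under Table 1: *Subject to the text above: if the next cycle was held more than 14 days for toxicity, reduce by 25%; no more than two reductions; no increase after a reduction.*

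This needs no new data, visits or patients. The cost is slightly less investigator discretion, because the full-dose option is no longer available after a next-cycle toxicity hold of more than 14 days. If the sponsor does want to keep full dose available after a long hold, the text should say so and name who may approve it.

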APPENDIX D. Schedule of Study Procedures

Table 6: Schedule of Procedures for Cohorts 1-12

Study Activity	Screening ¹	Treatment Cycle 1				Treatment Cycles After 1				Progression/ Relapse	EOT ²	Long-term FU ³
		D1	D8 ⁴	D15 ⁴	D22 ⁴	D1 ⁵	D8	D15	End of C2 ^{6,7}			
Signed ICD	X											
Medical history	X											
Physical examination	X	X ⁸				X ⁸					X	
Vital signs	X	X	X	X	X	X					X	
ECOG PS	X	X				X					X	
Height	X											
Weight	X	X				X					X	
Hematology ⁹	X	X	X	X	X	X	X	X			X	
CD4, CD8, and B-cell counts		X				X					X	
Coagulation	X											
Serum chemistry ¹⁰	X	X	X	X	X	X					X	
Urinalysis ¹¹	X	X				X					X	
β-hCG (WCBP)	X											
12-lead ECG	X										X	
Concomitant medications	X	Continuous										
AE assessment		Continuous										
Disease response assessment ¹²	X								X	X		
Blood for PK assessment ¹³		X		X								
Blood for PD assessment ¹⁴		X	X	X	X							
FF-10502-01 administration ¹⁵		X	X	X		X	X	X				

Study Activity	Screening ¹	Treatment Cycle 1				Treatment Cycles After 1				Progression/ Relapse	EOT ²	Long-term FU ³
		D1	D8 ⁴	D15 ⁴	D22 ⁴	D1 ⁵	D8	D15	End of C2 ^{6,7}			
Survival assessment		X	X	X	X	X	X	X	X	X	X	X
Tumor biopsy		X ¹⁶										

Abbreviations: AE, adverse event; β -hCG, beta human chorionic gonadotropin; C, cycle; CT, computed tomography; D, day; EDTA, ethylenediaminetetraacetic acid; ECG, electrocardiogram; ECOG PS, Eastern Cooperative Oncology Group Performance Status; EOT, end of treatment; FU, follow-up; ICD, informed consent documentation; MRI, magnetic resonance imaging; PD, pharmacodynamics; PK, pharmacokinetics; WBCP, women of childbearing potential.

¹ Screening to be performed within 28 days before Cycle 1, Day 1.

² End of Treatment visit should be 28 days from last dose of study drug (\pm 5 days).

³ Long-term follow-up consists of clinic visits or telephone calls every 3 months to assess survival status.

⁴ Day 8, 15, or 22 \pm 1 day.

⁵ Day 1 (window \pm 2 days).

⁶ Day 28 \pm 3 days.

⁷ And every 2 cycles thereafter.

⁸ Abbreviated physical exam.

⁹ Hematology collected at Screening, Cycle 1 Day 1 (only if not performed in the previous 72 hours), Days 8, 15 and 22, Day 1 of each subsequent cycle (within 3 days of Day 1 of each subsequent cycle), Day 8 and 15 of each cycle (pre-dose) and End of Treatment. See [Table 3](#) for tests to be conducted at each time point.

¹⁰ Serum chemistry collected at Screening, Cycle 1 Day 1 (only if not performed within the previous 72 hours), Days 8, 15 and 22, Day 1 of each subsequent cycle (within 3 days of Day 1 of each subsequent cycle) and End of Treatment. See [Table 3](#) for tests to be conducted at each time point.

¹¹ Urinalysis collected at Screening, Cycle 1 Day 1 (only if not performed within the previous 72 hours), Day 1 of each subsequent cycle (within 3 days of Day 1 of each subsequent cycle) and End of Treatment. See [Table 3](#) for tests to be conducted at each time point.

¹² Disease Response Assessment may include CT, MRI, and physical exam.

¹³ Peripheral blood collected in EDTA for PK assessment Cycle 1 Day 1, Day 15, pre-dose, immediately following cessation of infusion (within 15 minutes), between 1-2 hours post-infusion, and between 4-6 hours post-infusion.

¹⁴ Peripheral blood collected in sodium heparin for PD assessment pre-dose Cycle 1 Days 1, 8, and 15, and during the Day 22 visit.

¹⁵ Prescribed dose (mg/m²) Day 1, 8, 15 of each 28-day cycle. Phase 2a dose is FF-10502-01 90 mg/m² Day 1, 8, and 15 of each 28-day cycle.

¹⁶ Patients may consent to an optional tumor biopsy during screening or during Cycle 1. (Refer to Section [10.1.13](#)).

Table 7: Schedule of Procedures for Cohorts 13

		Treatment Cycle 1			Treatment Cycles After 1			Progression / Relapse	EOT ²	Long-term FU ³
Study Activity	Screening ¹	D1	D8 ⁴	D15 ⁵	D1 ⁶	D8	End of C2 ^{7,8}			
Signed ICD	X									
Medical history	X									
Physical examination	X	X ⁹			X ⁹				X	
Vital signs	X	X	X	X	X				X	
ECOG PS	X	X			X				X	
Height	X									
Weight	X	X			X				X	
Hematology ¹⁰	X	X	X	X	X	X			X	
CD4, CD8, and B-cell counts		X			X				X	
Coagulation	X									
Serum chemistry ¹¹	X	X	X	X	X				X	
Urinalysis ¹²	X	X			X				X	
β-hCG (WCBP)	X									
12-lead ECG	X								X	
Concomitant medications	X	Continuous								
AE assessment		Continuous								
Disease response assessment ¹³	X						X	X		
Blood for PK assessment ¹⁴		X	X							
Blood for PD assessment ¹⁵		X	X	X						
FF-10502-01 administration ¹⁶		X	X		X	X				

		Treatment Cycle 1			Treatment Cycles After 1			Progression / Relapse	EOT ²	Long-term FU ³
Study Activity	Screening ¹	D1	D8 ⁴	D15 ⁵	D1 ⁶	D8	End of C2 ^{7,8}			
Survival assessment		X	X	X	X	X	X	X	X	X
Tumor biopsy	X ¹⁷									

Abbreviations: AE, adverse event; β -hCG, beta human chorionic gonadotropin; C, cycle; CT, computed tomography; D, day; EDTA, ethylenediaminetetraacetic acid; ECG, electrocardiogram; ECOG PS, Eastern Cooperative Oncology Group Performance Status; EOT, end of treatment; FU, follow-up; ICD, informed consent documentation; MRI, magnetic resonance imaging; PD, pharmacodynamics; PK, pharmacokinetics; WBCP, women of childbearing potential

¹ Screening to be performed within 28 days before Cycle 1, Day 1.

² End of Treatment visit should be 28 days from last dose of study drug (\pm 5 days).

³ Long-term follow-up consists of clinic visits or telephone calls every 3 months to assess survival status.

⁴ Day 8 \pm 1 day.

⁵ Day 15 \pm 1 day.

⁶ Day 1 (window \pm 2 days).

⁷ Day 21 \pm 3 days.

⁸ And every 2 cycles thereafter.

⁹ Abbreviated physical exam.

¹⁰ Hematology collected at Screening, Cycle 1 Day 1 (only if not performed in the previous 72 hours), Days 8, and 15, Day 1 of each subsequent cycle (within 3 days of Day 1 of each subsequent cycle), Day 8 and 15 of each cycle (pre-dose) and End of Treatment. See [Table 3](#) for tests to be conducted at each time point.

¹¹ Serum chemistry collected at Screening, Cycle 1 Day 1 (only if not performed within the previous 72 hours), Days 8, and 15, Day 1 of each subsequent cycle (within 3 days of Day 1 of each subsequent cycle) and End of Treatment. See [Table 3](#) for tests to be conducted at each time point.

¹² Urinalysis collected at Screening, Cycle 1 Day 1 (only if not performed within the previous 72 hours), Day 1 of each subsequent cycle (within 3 days of Day 1 of each subsequent cycle) and End of Treatment. See [Table 3](#) for tests to be conducted at each time point.

¹³ Disease Response Assessment may include CT, MRI, and physical exam.

¹⁴ Peripheral blood collected in EDTA for PK assessment Cycle 1 Day 1, Day 8, pre-dose, immediately following cessation of infusion (within 15 minutes), between 1-2 hours post-infusion, and between 4-6 hours post-infusion.

¹⁵ Peripheral blood collected in sodium heparin for PD assessment pre-dose Cycle 1 Days 1, 8, and during the Day 15 visit.

¹⁶ Prescribed dose (mg/m²) Day 1 and 8 of each 21-day cycle. Phase 2a dose is FF-10502-01 90 mg/m² Day 1 and 8 of each 21-day cycle.

¹⁷ Patients may consent to an optional tumor biopsy during screening or during Cycle 1. (Refer to Section [10.1.13](#)).

